10.2. Appendix 2: Clinical Laboratory Tests

The tests detailed in [Table 10-1](#) will be performed by the laboratory chosen by the Sponsor or the Sponsor's designee. Subjects do not need to fast prior to laboratory testing. Refer to the Laboratory Manual for information on where testing should be performed (site, local laboratory, central laboratory).

A urine dipstick will be performed at the study site at scheduled visits as noted in the Schedule of Assessments ([Section 1.3](#)) and when a subject presents with symptoms of a urinary tract infection at Unscheduled Visits. If the urine dipstick is positive for leukocytes, nitrates, or blood cells, a urinalysis and culture/sensitivity testing will be performed.

A urine pregnancy test will be performed at the site for all women of childbearing potential. If the urine pregnancy test is positive, a serum pregnancy test will be performed.

Table 10-1 Clinical Laboratory Tests

Hematology	Chemistry	Urine Dipstick/ Urinalysis ^a	Other
Hematocrit	Albumin	Blood	Serum β -hCG ^b
Hemoglobin	Alkaline phosphatase	Glucose	Urine drug screen
Platelet count	ALT	Protein	Fecal calprotectin ^{c,d}
WBC (total and differential)	AST	Specific gravity	Serum tissue transglutaminase antibody (IgA) ^d
RBC	Bicarbonate	Microscopic exam (RBCs, WBCs, epithelial cells and bacteria)	Coagulation (INR/PT/APTT) ^g
	Calcium	pH	
	Chloride	Color	
	Creatinine ^e	Urine pregnancy test (β -hCG) ^b	
	Follicle-stimulating hormone		

Hematology	Chemistry	Urine Dipstick/ Urinalysis ^a	Other
	Glucose (fasting or non-fasting)		
	Lipase		
	Potassium		
	Sodium		
	Total bilirubin		
	Direct bilirubin ^f		
	Blood urea nitrogen		
	Total cholesterol		

APTT = activated partial thromboplastin time; ALT = alanine aminotransferase; AST = aspartate aminotransferase; β -hCG = β -human chorionic gonadotropin; INR = international normalized ratio; PT = prothrombin time; RBC = red blood cell count; WBC = white blood cell count

^a A sample for urinalysis and urine culture/sensitivity testing will be sent to the laboratory only if the urine dipstick performed at the site tests positive for the presence of leukocytes, nitrites, or blood cells.

^b Urine β -hCG will be tested for women of childbearing potential only. If urine β -hCG is positive, a serum β -hCG must be performed.

^c Optional at Screening only.

^d Performed at Screening only per inclusion criterion #8.

^e Estimated glomerular filtration rate will be calculated and reported by the central lab.

^f If total bilirubin is elevated above the upper limit of normal.

^g Only upon request from Principal Investigator (if ALT, AST and bilirubin are increased).

10.3. Appendix 3: Adverse Events: Definitions and Procedures for Recording, Evaluating, Follow-up, and Reporting

Definition of AE

AE Definition

An AE is any untoward medical occurrence in a clinical study subject, temporally associated with the use of study drug, whether or not considered related to the study drug.

An AE can therefore be any unfavorable and unintended sign (including an abnormal laboratory finding), symptom, or disease (new or exacerbated) temporally associated with the use of study drug.

AE of Special Interest

An AESI (serious or nonserious) is one of scientific and medical concern specific to the Sponsor's study drug or program, which warrants ongoing monitoring and rapid communication by the Investigator to the Sponsor or designee. Such an event might warrant further investigation in order to characterize and understand it. See [Section 8.4.7](#) for AESIs defined for this study.

Events Meeting the AE Definition

- Any abnormal laboratory test results (hematology, clinical chemistry, or urinalysis) or other safety assessments (eg, ECGs, radiological scans, vital signs measurements), including those that worsen from baseline, considered clinically significant in the medical and scientific judgment of the Investigator (ie, not related to progression of underlying disease)
- Exacerbation of a chronic or intermittent pre-existing condition including either an increase in frequency and/or intensity of the condition
- New condition detected or diagnosed after study drug administration even though it may have been present before the start of the study
- Signs, symptoms, or the clinical sequelae of a suspected drug-drug interaction
- Signs, symptoms, or the clinical sequelae of a suspected overdose of either study drug or a concomitant medication. For this study, report all overdose events within 24 hours of awareness by the study site, using the Overdose eCRF, whether or not the overdose is associated with an AE.
- Lack of efficacy or failure of expected pharmacological action per se will not be reported as an AE or SAE. Such instances will be captured in the efficacy assessments. However, the signs, symptoms, and/or clinical sequelae resulting from lack of efficacy will be reported as AEs or SAEs if they fulfill the definition of an AE or SAE. Any worsening of diarrhea or constipation and any new onset of constipation in IBS-D subjects should be collected as AEs.

Events NOT Meeting the AE Definition

- Abnormal screening laboratory values, including fecal calprotectin, C-reactive protein, etc.
- Any clinically significant abnormal laboratory findings or other abnormal safety assessments that are associated with the underlying disease, unless judged by the Investigator to be more severe than expected for the subject's condition. Merely repeating an abnormal test, in the absence of any of the above conditions, does not constitute an AE. Any abnormal test result that is determined to be an error does not require recording as an AE.
- The disease/disorder being studied or expected signs, or symptoms (clearly defined) of the disease/disorder being studied, unless more severe than expected for the subject's condition.
- Medical or surgical procedure (eg, endoscopy, appendectomy) the condition that leads to the procedure is the AE.
- Situations in which an untoward medical occurrence did not occur (social and/or convenience admission to a hospital).
- Anticipated day-to-day fluctuations of pre-existing disease(s) or condition(s) present or detected at the start of the study that do not worsen.

Definition of SAE

SAEs must meet both the AE criteria described above and the seriousness criteria listed below.

An SAE is defined as any untoward medical occurrence that, at any dose:**a. Results in death****b. Is life-threatening**

The term *life-threatening* in the definition of *serious* refers to an event in which the subject was at risk of death at the time of the event. It does not refer to an event, which hypothetically might have caused death, if it were more severe.

c. Requires inpatient hospitalization or prolongation of existing hospitalization

In general, hospitalization signifies that the subject has been admitted to the hospital or kept in the Emergency Room for ≥ 24 hours for observation and/or treatment that would not have been appropriate in the physician's office or outpatient setting. Complications that occur during hospitalization are AEs. If a complication prolongs hospitalization or fulfills any other serious criteria, the event is serious. When in doubt as to whether hospitalization occurred or was necessary, the AE should be considered serious.

Hospitalization for elective intervention of a pre-existing condition that did not worsen from baseline is not considered an AE.

d. Results in persistent disability/incapacity

The term disability means a substantial disruption of a person's ability to conduct normal life functions.

This definition is not intended to include experiences of relatively minor medical significance such as uncomplicated headache, nausea, vomiting, diarrhea, influenza, and accidental trauma (eg, sprained ankle) which may interfere with or prevent activities of daily living but do not constitute a substantial disruption.

e. Is a congenital anomaly/birth defect**f. Other situations:**

Medical or scientific judgment should be exercised in deciding whether SAE reporting is appropriate in other situations such as important medical events that may not be immediately life-threatening or result in death or hospitalization but may jeopardize the subject or may require medical or surgical intervention to prevent one of the other outcomes listed in the above definition. These events should usually be considered serious.

Examples of such medically significant events include invasive or malignant cancers, intensive treatment with a drug in an emergency room or at home for allergic bronchospasm, blood dyscrasias or convulsions that do not result in hospitalization, or development of drug dependency or drug abuse.

Recording and Follow-Up of AEs and SAEs

AE and SAE Recording

- When an AE or SAE occurs, it is the responsibility of the Investigator to review all documentation (eg, hospital progress notes, laboratory reports, and diagnostics reports) related to the event.
- The Investigator will then record all relevant AE or SAE information in the eCRF page.
- All SAEs (including serious AESIs) must be **reported in the eCRF within 24 hours of the study site personnel's knowledge of the event**, regardless of the Investigator assessment of the relationship of the event to study drug.
 - The event term, start date, severity, and initial causality assessment must be entered in the AE eCRF page and the event must be marked as “Serious”. This will activate additional assessment fields including “action taken with study drug”, “seriousness criteria”, and “brief description” which should be completed as soon as information is available. Marking the event as “serious” will automatically send required notifications for Sponsor or designee review.
 - The initial SAE report should include:
 - The date of the report
 - A description of the SAE (event term, seriousness of the event, date of onset, intensity)
 - Causal relationship to the study drug
 - A discharge summary should be provided for all hospitalizations. If the subject died, the report should include the cause of death as the event term (with death as the outcome) and whether the event leading to death was related to study drug, as well as the autopsy findings, if available
- Nonserious AESIs should be reported on the eCRF within 72 hours of knowledge of the information.
- It is **not** acceptable for the Investigator to send photocopies of the subject's medical records to the Sponsor or designee in lieu of completion of the AE or SAE eCRF.
- There may be instances when copies of medical records for certain cases are requested by the Sponsor or designee. In this case, all subject identifiers, with the exception of the subject number, will be redacted on the copies of the medical records before submission.
- The Investigator will attempt to establish a diagnosis of the event based on signs, symptoms, and/or other clinical information. Whenever possible, the diagnosis (not the individual signs/symptoms) will be documented as the AE/SAE.

Assessment of Intensity	
1/MILD	Asymptomatic or mild symptoms, clinical or diagnostic observations only; intervention not indicated.
2/MODERATE	Minimal, local, or noninvasive intervention indicated; limiting age-appropriate instrumental activities of daily living
3/SEVERE OR MEDICALLY SIGNIFICANT	Not immediately life-threatening; hospitalization or prolongation of hospitalization indicated; disabling; limiting self-care activities of daily living
4/LIFE-THREATENING	Life threatening consequences; urgent intervention indicated
5/DEATH	Death related to adverse event

An event is defined as *serious* when it meets at least one of the predefined criteria as described in the definition of an SAE, NOT when it is rated as severe.

Assessment of Causality	
The Investigator is obligated to assess the relationship between study drug and each occurrence of each AE or SAE.	
A reasonable possibility of a relationship conveys that there are facts, evidence, and/or arguments to suggest a causal relationship, rather than a relationship cannot be ruled out.	
The Investigator will use clinical judgment to determine the relationship.	
Alternative causes, such as underlying disease(s), concomitant therapy, and other risk factors, as well as the temporal relationship of the event to study drug administration will be considered and investigated.	
The Investigator will also consult the Investigator's Brochure and/or product information, for marketed products, in his/her assessment.	
For each AE or SAE, the Investigator must document in the medical notes that he/she has reviewed the AE or SAE and has provided an assessment of causality.	
There may be situations in which an SAE has occurred and the Investigator has minimal information to include in the initial report. However, it is very important that the Investigator always make an assessment of causality for every event before the initial transmission of the SAE to the Sponsor or designee.	
The Investigator may change his/her opinion of causality in light of follow-up information and send an SAE follow-up report with the updated causality assessment.	
The causality assessment is one of the criteria used when determining regulatory reporting requirements.	

Reporting of SAEs**SAE Reporting**

All SAEs must be **reported in the eCRF within 24 hours of the study site personnel's knowledge of the event**, regardless of the Investigator assessment of the relationship of the event to study drug. Marking the event as "Serious" will activate additional assessment fields.

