Visit Window		± 4 days		± 4 days	± 4 days	± 4 days	± 4 days	-7 days	Safety Follow-up call will occur 7 to 14 days after the last dose of study drug (includes window of -7 days) ^a
Laboratory assessments (chemistry, hematology, urine dipstick) ^b	X		X	X	X	X	X		Tests specified in Section 10.2
Serum tissue transglutaminase antibody (IgA)	X								Screening only
12-lead ECG	X								Screening only; supine
Dispense/collect subject diary		X Dispense					X Collect		Bowel Movement Diary will record bowel movement frequency and form, bowel urgency, and recurrent bowel movements; Pain Diary will record worst abdominal pain and use of rescue meds
Dispense Run-in study drug		X							Daily dosing
Administer witnessed dose of study drug		X	X						
Randomization			X						

	Screening	Run-in	Double-blind Treatment					Safety Follow-up	Notes
	Visit 1	Visit 2	Visit 3	Visit 4	Visit 5	Visit 6	Visit 7	Telephone Call	
Day/Week	Day -42 to -15	Day -14	Baseline Day 1	Week 2 (Day 15)	Week 4 (Day 29)	Week 8 (Day 57)	Week 12 or Early WD (Day 85)	Week 14 or 14 days after last dose (at the latest)	
Visit Window		± 4 days		± 4 days	± 4 days	± 4 days	± 4 days	-7 days	Safety Follow-up call will occur 7 to 14 days after the last dose of study drug (includes window of -7 days) ^a
Dispense new bottle of double-blind study drug for daily dosing			X		X	X			At Visit 4 (Week 2), the Visit 3 (Baseline) bottle will be checked for compliance and returned to subject
GIS			X	X	X	X	X		Before vital signs and blood draw
WPAI			X			X	X		Before vital signs and blood draw
IBS-QoL			X			X	X		Before vital signs and blood draw
Additional questions on abdominal pain (see Section 10.8.4)			X	X	X	X	X		Before vital signs and blood draw

AE = adverse event; avg = average; ECG = electrocardiogram; GIS = Global Improvement Scale; IBS = irritable bowel syndrome; IBS-QoL = irritable bowel syndrome quality of life; IWRS = interactive web response system; min = minutes; SAE = serious adverse events; WD = withdrawal; WPAI = Work Productivity and Activity Impairment

^a Safety Follow-up telephone call will occur only for randomized subjects who complete Week 12 or withdraw from the study early.

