8.3.2. Vital Signs

Vital signs, including blood pressure, pulse, body temperature, weight, and height, will be assessed at the timepoints specified in the Schedule of Assessments ([Section 1.3](#)) and [Section 10.7](#) as follows:

- Blood pressure and pulse will be measured after the subject has been resting in a seated position for 5 minutes, after PRO assessments and before any blood draws.
- Blood pressure measurements will be taken on the same arm and by the same site staff throughout the study, if possible.
- Sitting systolic and diastolic blood pressures will be determined by averaging 3 replicate measurements obtained 1 to 2 minutes apart. The average of the 3 measurements will be used for eligibility and safety assessments.
- The same method for assessing temperature should be used at all visits for a particular subject.
- Body weight will be measured with subjects in street clothing with jacket/coat and shoes removed, using the same scale throughout the study, if possible.
- Standing height will be measured without shoes, at Screening only.

8.3.3. *Electrocardiograms*

At Screening only, a 12-lead ECG will be performed in the supine position using an ECG machine that automatically calculates the heart rate and measures PR, QRS, QT, and QTc intervals. ECGs will be read by trained personnel at the study site.

8.3.4. *Clinical Safety Laboratory Assessments*

All protocol-required laboratory assessments, as defined in [Section 10.2](#) and including urine pregnancy test and drug screen, must be conducted in accordance with the laboratory manual and the Schedule of Assessments ([Section 1.3](#)). Repeat or unscheduled samples may be taken for safety reasons or for technical issues with the samples.

The clinical significance of test results will be evaluated as follows:

- At Screening, the Investigator or physician sub-investigator will assess the clinical significance of any values outside the reference ranges provided by the laboratory, and subjects with abnormalities judged to be clinically significant will be excluded from the study.

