8.4.3. Follow-up of Adverse Events and Serious Adverse Events

After the initial AE or SAE report, the Investigator is required to proactively follow each subject at subsequent visits/contacts. All AEs will be followed until the Week 14 Safety Follow-up telephone call (14 days [with a -7-day window] after the last dose of study drug). All SAEs will be followed until resolution, stabilization, the event is otherwise explained, or the subject is lost to follow-up (as defined in [Section 7.3](#)). If a subject dies during participation in the study or

within 14 days of the last dose of study drug, the Investigator will provide the Sponsor or designee with a copy of any postmortem findings including histopathology.

The Investigator is obligated to perform or arrange for the conduct of supplemental measurements and/or evaluations as medically indicated or as requested by the Sponsor or designee to elucidate the nature and/or causality of the AE or SAE as fully as possible. This may include additional laboratory tests or investigations, histopathological examinations, or consultation with other health care professionals.

New or updated information will be recorded in the originally completed eCRF. As noted above, the Investigator will submit any updated SAE data within 24 hours of receipt of the information.

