8.4.7. Adverse Events of Special Interest

Selected nonserious and serious AEs will be reported as AESIs. The events must be reported on the AE eCRF within 24 hours of the study site personnel's knowledge of the event. AESIs that also meet the definition of an SAE must be reported as described in [Section 10.3](#).

Adverse events of clinical interest for this study include:

- Potential major cardiac and cerebrovascular events, including death (or any event with fatal outcome), myocardial infarction, cerebrovascular accident, hospitalization for unstable angina or chest pain, hospitalization for heart failure, and coronary revascularization/angioplasty/stent
- Hypertension, defined as follows:
 - [REDACTED]

- [REDACTED]
- [REDACTED]
- AEs consistent with orthostatic hypotension as confirmed by orthostatic vital signs
- AEs suggestive of cystitis or urinary tract infection (UTI)
- [REDACTED]
- [REDACTED]
- [REDACTED]
- [REDACTED]

- Elevated aspartate aminotransferase (AST) or alanine aminotransferase (ALT) lab value requiring that study drug be temporarily withheld or permanently discontinued (see [Sections 8.4.7.1](#) and [8.4.7.2](#)). To date, no concern regarding drug-induced liver toxicity has been identified; however, the Sponsor is monitoring laboratory data for a potential safety signal, consistent with Food and Drug Administration (FDA) guidance [[FDA Guidance, 2009](#)].

Serious AESIs and elevated liver enzymes or bilirubin requiring withholding of study drug must be reported within 24 hours of the study site personnel's knowledge of the event by marking the appropriate box on the AE eCRF and assigning the most appropriate category. Additional information should be provided as directed in the eCRF Completion Guidelines. AESIs that also meet the definition of an SAE must be reported as an SAE, as described in [Section 8.4.4](#). Nonserious AESIs should be reported within 72 hours of the site personnel's knowledge, using the AE eCRF.

8.4.7.1. Criteria for Temporary Withholding of Study Drug in Association with Liver Test Abnormalities

Elevated liver enzymes or bilirubin sufficient to require withholding study medication must be reported **within 24 hours of the study site personnel's knowledge of the event** using AESI -specific eCRFs/forms/worksheets provided for the study.

Hepatic enzymes will be monitored in accordance with FDA drug-induced liver injury guidelines [[FDA Guidance, 2009](#)].

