If **any** of the following liver test abnormalities develop, study drug should be withheld immediately with appropriate clinical follow-up (including repeat laboratory tests, until a subject's laboratory profile has returned to normal/baseline status), and the event reported as an SAE:

- ALT or AST $> 8 \times$ upper limit of normal (ULN)
- ALT or AST $> 5 \times$ ULN and persists for more than 2 weeks
- ALT or AST $> 3 \times$ ULN and total bilirubin $> 2 \times$ ULN or international normalized ratio (INR) > 1.5
- ALT or AST $> 3 \times$ ULN with appearance of fatigue, nausea, vomiting, right upper quadrant pain or tenderness, fever, rash and/or eosinophilia ($> 5\%$)

Rechallenge may be considered if an alternative cause for the abnormal liver tests (ALT, AST, total bilirubin) is discovered and the laboratory abnormalities resolve to normal or baseline values. The Investigator and Sponsor's designated Medical Monitor must discuss and agree with any decision to rechallenge.

Rechallenge should not occur when the etiology of the liver test abnormalities is considered possibly drug-induced.

8.4.7.2. Criteria for Permanent Discontinuation of Study Drug in Association with Liver Test Abnormalities

Study drug should be discontinued permanently if **all** of the following 4 criteria are met (ie, potential severe drug-induced liver injury/Hy's law case):

- Total bilirubin increases to $> 2 \times$ ULN or INR > 1.5 **and**
- AST or ALT increases to $\geq 3 \times$ ULN **and**
- Alkaline phosphatase value does not reach $2 \times$ ULN **and**
- No alternative cause explains the combination of the above laboratory abnormalities; important alternative causes include, but are not limited to, the following:
 - Hepatobiliary tract disease
 - Viral hepatitis (eg, hepatitis A/B/C/D/E, Epstein-Barr virus)
 - Exposure to hepatotoxic agents/drugs or hepatotoxins, including herbal and dietary supplements, plants, and mushrooms;
 - Alcoholic hepatitis
 - Non-alcoholic steatohepatitis

- Autoimmune hepatitis

If an alternative cause for hepatotoxicity is identified, then it should be determined (based on the severity of the hepatotoxicity or event) whether study drug should be withheld or permanently discontinued as appropriate for the safety of the subject, following consultation with the Sponsor's designated Medical Monitor.

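### INR > 1.5 can trigger withholding or stopping study drug, but neither document requires an INR when ALT or AST reaches 3 x ULN

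*Protocol*

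**What the plan says.** Protocol 8.4.7.1 lists four liver abnormalities, any one of which requires study drug to be withheld at once and the event reported as an SAE. The third combines ALT or AST > 3 x ULN with bilirubin > 2 x "ULN or international normalized ratio (INR") > 1.5. Protocol 8.4.7.2 requires permanent discontinuation when four conditions all hold. The first is bilirubin > 2 x "ULN or INR > 1.5"; the others are AST or ALT >= 3 x ULN, alkaline phosphatase below 2 x ULN, and no alternative cause.

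The scheduled panel in Protocol 1.3 is "Laboratory assessments (chemistry, hematology, urine dipstick"), with no coagulation test. INR/PT/APTT appears in Table 10-1 under the miscellaneous column with footnote g: "Only upon request from Principal Investigator (if ALT, AST and bilirubin are increased"). SAP 7.4 carries the same footnote. In the same table, footnote f gives direct bilirubin a definite trigger: "If total bilirubin is elevated above the upper limit of normal".

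SAP 7.4 selects potential Hy's law subjects by ALT or AST >= 3 x ULN with bilirubin >= 2 x ULN. INR is not used.

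**The concern.** A stopping rule works only if its inputs are measured when they matter. Here INR is written in as a substitute for bilirubin, yet the clause governing the test makes it conditional on bilirubin already being raised. The footnote also names ALT and AST together, where the rules need only one of them.

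At stake is subject protection. A woman without symptoms whose ALT or AST is at least 3 x ULN and whose bilirubin is normal could meet the INR part of either rule without anyone knowing, and dosing would continue. The event would also go unrecognised as an SAE, and as the adverse event of special interest defined by transaminase elevation requiring withholding or discontinuation.

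**Working it through.** The plan states no figure to reproduce on this point. The check is a comparison of clauses and a count of visits.

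**Visits (Protocol 1.3).** Chemistry is scheduled at Visits 1, 3, 4, 5, 6 and 7, which is 6 visits. Visits 4 to 7 follow the first double-blind dose, which is 4 visits. INR is scheduled at 0 of 6. That would be acceptable for a triggered test, so the question is whether the trigger works.

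**When INR matters.** I read the withholding criterion as transaminase > 3 x ULN together with either bilirubin > 2 x ULN or INR > 1.5, which is how 8.4.7.2 is laid out. INR can then change the outcome only when bilirubin is <= 2 x ULN. Take 'increased' in footnote g to mean above ULN; the protocol does not define it. For a woman with ALT or AST at the rule's threshold:

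| Situation | Does the rule need INR? | What footnote g gives |
|---|---|---|
| Bilirubin normal | Yes | Condition not met; no INR provided for |
| Only one transaminase raised, bilirubin <= 2 x ULN | Yes | Condition not met as worded |
| Both transaminases raised, bilirubin above 1 and up to 2 x ULN | Yes | Optional, on investigator request |
| Bilirubin > 2 x ULN | No, bilirubin already satisfies this part | At most optional |

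INR is mandatory in no row. If the footnote is read loosely, as meaning that the liver panel is raised, the first two rows move from not provided for to optional. INR is still not required.

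**Other clauses that could lead to an INR.**
- Protocol 8.3.4: "Repeat or unscheduled samples may be taken for safety reasons or for technical issues with the samples". This is permission.
- Protocol 8.4.3 obliges the investigator to arrange "supplemental measurements and/or evaluations as medically indicated or as requested by the Sponsor or designee". This is a duty, but it sets no threshold and names no test.
- Protocol 8.4.7.1: "Hepatic enzymes will be monitored in accordance with FDA drug-induced liver injury guidelines". This concerns enzymes and cites an outside source.
- The repeat tests in 8.4.7.1 start after a criterion has been met, so they cannot supply the INR needed to meet it.

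None of these names INR or ties it to 3 x ULN.

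**SAP selection.** The protocol's Hy's law definition accepts bilirubin or INR, whereas SAP 7.4 accepts bilirubin only. A case qualifying through INR would be absent from the two outputs built on that selection, listing 14.3.3.8 and figure 14.3.3.3. If detected, it would have to be reported as an SAE and would appear in the SAE listings. The INR value would presumably be in listing 16.2.3.9, judging by that listing's title.

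**The case against.** The strongest reply is that the protocol leaves several routes to an INR and to stopping the drug without one. Protocol 7.1 lets the investigator discontinue for abnormal liver function whenever that is judged best for the subject. Protocol 8.3.4 calls for clinically significant results to be repeated until they settle, with the cause to be identified and the Medical Monitor told if they do not; it also anticipates local tests outside the protocol, so footnote g does not forbid an INR. Immediate safety concerns go to the Medical Monitor. The Laboratory Manual, the liver-event worksheets, the eCRF guidelines and the cited FDA guidance are not available here and may contain a trigger.

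These points limit the practical risk and the reach of the claim: the gap is shown for the protocol and SAP text only. They do not close it, because each route depends on judgement, on a request, or on a source not seen.

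Two further points stand. INR can complete the withholding criterion, but for permanent discontinuation it satisfies only one of four conditions. And the SAP display is a descriptive screen that also omits alkaline phosphatase and alternative cause, so it was never an exact copy of the stopping rule. Leaving those out widens the screen, however, while leaving out INR narrows it and can drop a case that the protocol defines as Hy's law.

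**Conclusion.** The concern holds, as a minor point. Footnote g conflicts with the rules it should serve: INR is neither scheduled nor required anywhere in the range where it could decide the matter.

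The exposed group is narrow: no listed symptoms or eosinophilia, ALT or AST from 3 to 8 x ULN and not above 5 x ULN for more than 2 weeks, bilirubin <= 2 x ULN, INR > 1.5, and no INR ordered. Women entering with ALT or AST > 2 x ULN are excluded, and the other withholding criteria catch elevations outside these limits. The documents give no basis for a rate. Two SAP outputs are affected, and efficacy is not.

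The conclusion rests on the text of the two documents, on 'increased' meaning above ULN, and on there being no trigger in the unseen manual, forms or guidance. Had such a trigger existed, footnote g would still need to be brought into line with it.

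**What to change.** Reword footnote g in Protocol Table 10-1 and in SAP 7.4 so that INR is required whenever ALT or AST is >= 3 x ULN, regardless of bilirubin, as a triggered test like direct bilirubin in footnote f. Using >= 3 covers both rules, since withholding starts above 3 x ULN and permanent discontinuation at 3 x ULN. In SAP 7.4, extend the potential Hy's law selection to bilirubin >= 2 x ULN or INR > 1.5; listing 14.3.3.8 and figure 14.3.3.3 then follow.

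The cost is a change of wording in two footnotes and one selection rule, plus a blood test already listed in the protocol for the few women with raised transaminases. Nothing changes in the efficacy analysis.
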